7.2.2 Vital Signs

At the time points indicated in the Schedule of Assessments ([Table 2](#)), evaluation of vital signs shall be performed after approximately 10 minutes rest in the sitting position. It shall include measurement of systolic and diastolic blood pressure, heart rate, and respiratory rate. Vital signs will be taken prior to any blood draw, excluding post-treatment measurements on Day 0.

 GALDERMA	Title 43QMI902 Clinical Study Protocol - QM1114 - LCL and GL	Doc id MA-40371
--	---	----------------------------------

All abnormal values at the baseline visit identified, as clinically significant by the Investigator, shall be recorded in the Medical History form.

For any clinically significant changes from the baseline visit, an AE is to be recorded.

7.2.3 **Electrocardiogram (ECG)**

The 12-lead ECG recordings will be made after the subjects have been resting in a supine position for at least 10 minutes at the time points indicated in [Table 2](#), the baseline ECG should be done prior to treatment. The subjects should avoid postural changes during the ECG recordings. At each time-point, the ECG will be recorded in triplicate. The triplicates will be performed at approximately one-minute intervals.

ECGs will be stored electronically and submitted to a central reviewer for analysis. Paper printouts may also be collected for general cardiac safety monitoring at the clinical research site.

Clinically significant abnormal values at baseline shall be recorded in the Medical History form. For any clinically significant changes from baseline, an AE is to be recorded.

The Investigator and Medical Monitor will be alerted (eg, email) for ECGs that are identified as “abnormal, clinically significant” by the central ECG laboratory.

7.2.4 **Laboratory Safety Tests**

Blood samples will be collected at baseline (prior to treatment) and at Month 6/ET, and sent to a central laboratory for analysis. Instructions for blood sampling are detailed in a separate laboratory manual.

The following laboratory safety tests shall be performed:

- Hematology: White blood cell (WBC) count with differential, red blood cell (RBC) count, haemoglobin (Hb), hematocrit (hct), and platelet count (Plt)
- Blood chemistry: Creatinine, urea nitrogen, gamma glutamyl transferase (GGT), alkaline phosphatase (ALP), aspartate aminotransferase (AST=SGOT), alanine aminotransferase (ALT=SGPT), and bilirubin (total and conjugated)

The Investigator or a medically qualified sub-Investigator must review and evaluate laboratory values for each subject in a timely manner. The Investigator or designee will initial and date all laboratory reports and note on the report whether or not an out of range laboratory value is clinically significant. An out of range laboratory value should be considered as clinically significant if either of the following conditions is met:

- The abnormality suggests a disease and/or organ toxicity.
- The abnormality is of a degree that requires additional active management, e.g. close observation, more frequent follow-up assessments, or further diagnostic investigation

 GALDERMA	Title 43QMI902 Clinical Study Protocol - QM1114 - LCL and GL	Doc id MA-40371
--	---	----------------------------------

2020-06-09 07:02

Effective date:

Effective

Version: 4.0

For each out of range laboratory result, the Investigator or designee will enter directly in the eCRF the Investigator judgment on the presence or the absence of a clinical significance.

All clinically significant out-of-range laboratory values for blood samples collected at baseline will be recorded in the medical history (report a diagnosis rather than an individual laboratory parameter abnormality whenever possible).

All clinically significant out of range laboratory values for blood samples collected after baseline are to be reported as an AE if this abnormality was not present at the baseline visit or is assessed as having worsened since the screening visit (i.e., there is a significant change from baseline).

For AEs, whenever possible, the Investigator is to provide a diagnosis rather than to report individual laboratory abnormalities.

7.2.5 Neutralizing Antibody Testing

Subjects will have blood samples taken at baseline prior to treatment, Month 1, and Month 6/ET for measurement of serum neutralizing antibody testing against QM1114-DP.

Additional information and detailed description of sample volumes, processing, and storage requirement will be included in a Laboratory Manual.

7.2.6 Adverse Events

AEs are to be monitored throughout the course of the clinical study from the time the informed consent form has been signed. All AEs are to be reported on the AE form of the eCRF with complete information as required.

If AEs occur, the main concern shall be the safety of the subjects. At the time of the ICF signature, each subject must be provided with the name and phone number of clinical study center personnel for reporting AEs and medical emergencies.

At each post enrollment visit, the Investigator (or sub-Investigator) will question the subject about AEs using an open non-persuasive question to elicit reporting of AEs, for example "Have you noticed any change in your health since the last visit?" Additional questioning and examination will then be performed as appropriate.

7.2.6.1 Definitions

7.2.6.1.1 Adverse Events (AE)

According to ICH E2A,¹⁵ an AE is any untoward medical occurrence in a patient or a clinical investigation subject administered a pharmaceutical product and which does not necessarily have a causal relationship with this treatment. An AE can therefore be any unfavorable and unintended sign (including an abnormal laboratory finding), symptom, or disease temporally associated with the use

 GALDERMA	Title 43QMI902 Clinical Study Protocol - QM1114 - LCL and GL	Doc id MA-40371
--	---	----------------------------------

Effective date: 2020-06-09 07:02

Effective

Version: 4.0

of a medicinal (investigational) product, whether or not related to the medicinal (investigational) product.

Thus, any new sign, symptom or disease, or any clinically significant worsening of an existing sign, symptom or disease (including new episodes of a chronic disease [e.g., hay fever, allergy]) compared to the condition at the first visit, should be considered as an AE. Lack of efficacy is not considered as an AE.

Notes:

- There should be an attempt to report a diagnosis rather than the signs, symptoms or abnormal laboratory values associated with the report of an AE. However, a diagnosis should be reported only if, in the Investigator's judgment, it is relatively certain. Otherwise, symptoms, signs, or laboratory values should be used to describe the AE.
- Pregnancy is not to be considered as an AE; however, is an important medical event that must be monitored as described in Section [7.2.6.2.3](#).
- The effects of all BoNT products may spread from the area of injection to produce symptoms consistent with BoNT effects. These symptoms have been reported hours to weeks after injection. Remote spread of toxin that affects swallowing and breathing can be life threatening, and there have been reports of death. The risk of symptoms is increased in subjects who have underlying conditions (e.g. disorders of the neuromuscular junction) that would predispose them to these symptoms. BoNT is contraindicated in individuals with known hypersensitivity to any BoNT preparation or to any of the components in the formulation.

7.2.6.1.2 *Treatment Emergent Adverse Event (TEAE)*

A TEAE is an event that emerges during treatment, having been absent pre-treatment, or worsens relative to the pretreatment state.

7.2.6.1.3 *Serious Adverse Events (SAE)*

A SAE is any untoward medical occurrence that at any dose:

- Results in death,
- Is life-threatening,
- Requires inpatient hospitalization or prolongation of existing hospitalization,
- Results in persistent or significant disability/incapacity, or
- Is a congenital anomaly/birth defect.

Important medical events that may not result in death, be life-threatening, or require hospitalization may be considered an SAE when, based upon appropriate medical judgment, they may jeopardize the safety of the subject, and may require medical or surgical intervention to prevent one of the outcomes listed in this definition. Examples of such events are intensive treatment in an emergency room or at home for allergic bronchospasm, blood dyscrasia, or convulsions that do not result in hospitalization.

 GALDERMA	Title 43QMI902 Clinical Study Protocol - QM1114 - LCL and GL	Doc id MA-40371
--	---	----------------------------------

Effective date: 2020-06-09 07:02

Effective date:

Effective

Version: 4.0

Note: The term “life-threatening” refers to an event in which the subject was at risk of death at the time of the event; it does not refer to an event which hypothetically might have caused death if it were more severe.

Inpatient hospitalization is considered to have occurred if the subject has had to stay for a night at the hospital. The criterion for prolongation of hospitalization is also defined as an extra night at the hospital. Hospitalization may not constitute sufficient grounds to be considered as an SAE if it is solely for the purpose of a diagnostic test(s) (even if related to an AE), elective hospitalization for an intervention that was already planned before subject enrolment in the clinical study, admission to a day-care facility, social admission (e.g., if the subject has no place to sleep), or administrative admission (e.g., for a yearly examination).

7.2.6.1.4 *Unexpected Adverse Drug Reaction*

An unexpected adverse drug reaction is defined as an adverse reaction, the nature or severity of which is not consistent with the applicable study product information (e.g., Investigator's Brochure for an unapproved investigational product or the medicinal package insert/summary of product characteristics for an approved investigational product).

7.2.6.1.5 *Adverse Event Reporting Period*

The clinical study period during which AEs must be reported is the period from when the subject signed the ICF to the end of the subject's participation.

The Sponsor should be informed if the Investigator becomes aware of any unusual safety information or any safety information that appears to be drug-related involving a subject who has participated in a clinical study, even after a subject has completed the clinical study.

7.2.6.1.6 *Severity*

Severity is a clinical determination of the intensity of an AE and not the severity of a disease.

The Investigator is to classify the intensity of AEs using the following definitions as a guideline. For this classification, the Investigator will take into account the possible range of the intensity of the event and report the grade of intensity which is the most appropriate according to his/her medical judgment.

Mild	Awareness of signs or symptom, but easily tolerated.
Moderate	Discomfort, enough to cause interference with usual activity.
Severe	Incapacitating with inability to work or perform usual activity.

7.2.6.1.7 *Relationship to the Study Product and/or Clinical Study Procedure*

The Investigator is to determine whether there is a reasonable causal relationship between the occurrence of the AE and exposure to the study product and/or clinical study procedure.

 GALDERMA	Title 43QMI902 Clinical Study Protocol - QM1114 - LCL and GL	Doc id MA-40371
--	---	----------------------------------

Effective date: 2020-06-09 07:02

Effective

Version: 4.0

Medical judgment should be used to determine the relationship, considering all relevant factors including the pattern of reaction, temporal relationships, relevant medical history, and confounding factors such as co-medication or concurrent diseases.

The expression “reasonable causal relationship” is meant to convey in general that there are facts or arguments to suggest a causal relationship (ICH E2A, Section IIIA 1).

The relationship assessment for an AE is to be completed using the following definitions as a guideline:

Reasonable Possibility: According to the reporting Investigator, there is a reasonable possibility (i.e., suggestive evidence or arguments) that there is a causal relationship irrespective of the dose administered between:

- The study product (active or placebo) and the AE.
- The clinical study protocol procedure (e.g., bruising or marks from blood draws, injection related trauma, etc.) and the AE.

A two-point scale (Yes or No response) shall be used for the causality assessment. The Investigator shall be asked to indicate a response to each of the following questions in the eCRF:

- “Do you consider that there is a reasonable possibility that the event may have been caused by the study product?”, and
- “Do you consider that there is a reasonable possibility that the event may have been caused by the study product injection procedure?”

If any of these questions is answered Yes, the AE is considered related.

No Reasonable Possibility: No suggestive evidence or arguments can be identified regarding a causal relationship between the study product or the clinical study protocol procedure and the AE.

7.2.6.2 Reporting Procedures

7.2.6.2.1 Procedures for Reporting Adverse Events

The collection of AEs is from the time that a subject signs the ICF to their final visit.

At each post-enrollment visit, the Investigator (or sub-Investigator) will question the subject about AEs using an open non-persuasive question to elicit reporting of AEs, for example “Have you noticed any change in your health since the last visit?” Directed questioning and examination will then be performed as appropriate.

Any AE occurring during the AE reporting period, whether it is related to the study product or not, will be recorded immediately in the source document, and described on the AE form of the eCRF along with the date of onset, severity, relationship to the study product, and outcome, without omitting any requested and known information. Additional information will be requested under certain circumstances.

 GALDERMA	Title 43QMI902 Clinical Study Protocol - QM1114 - LCL and GL	Doc id MA-40371
--	---	----------------------------------

Effective date: 2020-06-09 07:02

Effective date:

Effective

Version: 4.0

At study end, AEs assessed as related to the treatment or study procedure will be monitored until they have resolved or reached a stable condition. Other AEs will be monitored until the last visit if they have not resolved or reached a stable condition.

The Investigator will maintain all pertinent medical records in the subject's study file. If necessary and approved by the subject or their legal health care representative, the Investigator may contact the subject's personal physician or other health care provider(s) to obtain further details.

For SAEs (see Section 7.2.6.2.2) and pregnancies (see Section 7.2.6.2.3), the Sponsor is to be informed immediately by e-mail. The event must be reported by to the Safety email within 24 hours of receipt of the information (contact details in Section 7.2.6.2.2).

7.2.6.2.2 *Procedure for Reporting a Serious Adverse Event*

For a SAE occurring during the clinical study, regardless of whether it is related to the treatment or not, and of whether it is expected or not, the Investigator must do the following:

1. Take prompt and appropriate medical action, if necessary. The safety of the subject is the first priority.
2. Ensure that the event is classified as an SAE (Section 7.2.6.1.3).
3. Complete the AE form provided in the eCRF as fully as possible.

Print and complete the SAE form. E-mail the completed form, accompanied by any other relevant information or anonymized medical records (e.g., laboratory test results) within 24 hours of receipt of the information to Safety e-mail listed below. The demographics, medical history, drugs/therapies form, medical and surgical procedures form, and AE pages of the eCRF must be completed and available for review in the EDC system at the time of the report.

4. Immediately send the completed SAE report form to the Safety e-mail and discuss further actions to be taken.

E-mail: **PPD**

Additional contact details are provided in the Investigator's site file.

5. Monitor and record the progress of the event until it resolves or reaches a clinically stable outcome, with or without sequelae. For all additional follow-up evaluations, send all additional follow-up information on the SAE to the Safety e-mail within 24 hours of receipt of the updated information. SAEs will be monitored until the Investigator and Sponsor agree that the event is satisfactorily resolved.
6. Obtain and maintain in his/her files all pertinent medical records and information regarding the SAE.

 GALDERMA	Title 43QMI902 Clinical Study Protocol - QM1114 - LCL and GL	Doc id MA-40371
--	---	----------------------------------

Effective date: 2020-06-09 07:02

Effective

Version: 4.0

7. Inform the Sponsor of the final outcome of the event. Send a follow-up SAE form, when appropriate, to the Safety e-mail.
8. Prompt notification of SAEs by the Investigator to the Sponsor is essential so that legal obligations and ethical responsibilities towards the safety of subjects are met. The Sponsor has a legal responsibility to notify both the local regulatory authority and other regulatory agencies about the safety of a product under clinical investigation. The Sponsor will comply with country specific regulatory requirements relating to safety reporting to regulatory authorities, Institutional Review Boards (IRBs), and Investigators. Investigator safety reports are prepared for Suspected Unexpected Serious Adverse Reactions (SUSARs) according to local regulatory requirements and the Sponsor policy and are forwarded to Investigators as necessary. An Investigator who receives an Investigator safety report describing a SAE(s) or other specific safety information (e.g., summary or listing of SAEs) from the Sponsor will file it with the Investigator's Brochure (IB) and will notify the IRB, if appropriate according to local requirements.
9. Comply with the applicable regulatory requirement(s) related to the reporting of SAEs to the IRB.

7.2.6.2.3 *Procedures for Reporting Pregnancies*

Any pregnancy occurring during the clinical study, where the fetus could have been exposed to the study product, must be monitored until its outcome in order to ensure the complete collection of safety data.

Subjects who become pregnant during the screening period are considered as screening failures; they are recorded as such in the eCRF and no pregnancy form is to be completed.

If a subject becomes pregnant after the screening period, the Investigator is to do the following:

1. The subject does not need to be withdrawn from the clinical study, i.e. she may continue to attend the planned study visits, but no invasive procedure should be conducted (e.g. no sample taken for lab test).
2. Complete the Pregnancy Report Part A as fully as possible. Send the form within 24 hours of receipt of the information to the Safety e-mail listed above (and in Section 11.9).
3. Monitor and record the progress of the pregnancy until its outcome. If necessary and approved by the subject or their legal health care representative, contact the subject's regular physician (general practitioner or gynecologist) or hospital staff to obtain further details and ask for regular follow up information.
4. At the outcome of the pregnancy, complete the Pregnancy Report Part B. For all the additional evaluations, send the follow-up information to the Safety e-mail within 24 hours of receipt of the information. If the subject can no longer be reached (lost to follow-up), documentation of the non-response/contact with two phone calls and a letter (certified with return receipt) is required.

 GALDERMA	Title 43QMI902 Clinical Study Protocol - QM1114 - LCL and GL	Doc id MA-40371
--	---	----------------------------------

5. If the pregnancy leads to an abortion (voluntary abortion, spontaneous abortion or therapeutic abortion), *in utero* death or congenital anomaly, follow the procedure for declaration of an SAE (see Section 7.2.6.2.2).

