3. OVERALL CLINICAL STUDY DESCRIPTION

This is a phase 3, multicenter, randomized, double-blind, placebo-controlled, parallel-group study with treatment of QM1114-DP in the LCL and GL, alone or in combination.

Following the informed consent and the screening process, eligible subjects will be randomly assigned to treatment in a 2:2:2:1 ratio. Subjects will receive a single treatment at baseline (Day 0) of either:

- 60 units QM1114-DP (60 units in the LCL and placebo in the GL, 118 subjects),
- 50 units QM1114-DP (50 units in the GL and placebo in the LCL, 118 subjects),
- 110 units QM1114-DP (60 units in the LCL and 50 units in the GL, 118 subjects), or
- Placebo in both the LCL and GL (59 subjects).

Randomization will be stratified by study center.

Subjects eligible for the treatment must meet the severity criteria for LCL and GL at baseline (i.e. moderate to severe LCL and GL at maximum smile and maximum frown, respectively). LCL should be bilaterally symmetrical. Baseline wrinkle severity determination will be based on both investigator and subject ratings using the 4-point photographic scale of LCL severity (LCL-ILA; LCL-SLA) and the 4-point photographic scale of GL severity (GL-ILA) and the subject 4-point categorical scale (GL-SLA).

[figure not shown]
 GALDERMA	Title 43QMI902 Clinical Study Protocol - QM1114 - LCL and GL	Doc id MA-40371
--	---	----------------------------------

Following treatment at baseline, subjects will be monitored for safety and efficacy according to the Schedule of Assessments ([Table 2](#)).

Efficacy assessments will include (Section [7.1](#)):

- Investigator 4-point Photographic Scale of LCL Severity at **CCI** maximum smile (Investigator assessment [LCL-ILA])
- Subject 4-point Photographic Scale of LCL Severity at **CCI** maximum smile (subject assessment [LCL-SLA])
- Investigator 4-point Photographic Scale of GL Severity at **CCI** maximum frown (Investigator assessment [GL-ILA])
- Subject Static 4-point Categorical Scale of GL Severity at maximum frown (subject assessment [GL-SLA])

CCI

Safety assessments will include (Section [7.2](#)):

- AEs
- Focused physical examination (FPE)
- Vital signs
- ECG
- Laboratory safety tests (chemistry and hematology)
- Production of neutralizing antibodies against QM1114-DP

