1.1 Background

1.1.1 Study design

This is a phase 3, multicenter, randomized, double-blind, placebo-controlled, parallel-group study with treatment of QM1114-DP in the LCL and GL, alone or in combination.

Each subject will receive a single treatment of:

- 60 units QM1114-DP (60 units in the LCL and placebo in the GL),
- 50 units QM1114-DP (50 units in the GL and placebo in the LCL),
- 110 units QM1114-DP (60 units in the LCL and 50 units in the GL), or
- Placebo in both the LCL and GL.

Following treatment at baseline, subjects will be monitored for efficacy and safety over a period of approximately 6.5 months.

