14.3 Safety Data			
14.3.1 - 14.3.6 Exposure and Adverse Events			
14.3.1	Injection Administration and Characteristics	Safety	U
14.3.2	Overall Summary of Adverse Events	Safety	U

Table Number	Table Title	Analysis Population	(U)nique/ (R)epeat
14.3.3.1	Treatment Emergent Adverse Events by MedDRA System Organ Class and Preferred Term	Safety	U
14.3.3.2	Serious Treatment Emergent Adverse Events by Intensity, MedDRA System Organ Class and Preferred Term	Safety	U
14.3.3.3	Treatment Emergent Adverse Events Related to Study Product or Injection Procedure by Intensity, MedDRA System Organ Class and Preferred Term	Safety	R
14.3.3.4	Treatment Emergent Adverse Events That Led to Discontinuation by Intensity, MedDRA System Organ Class and Preferred Term	Safety	R
14.3.3.5	Treatment Emergent Adverse Events Unrelated to Study Product or Injection Procedure by Intensity, MedDRA System Organ Class and Preferred Term	Safety	R
14.3.3.6	Treatment Emergent Adverse Events Related to Study Product or Injection Procedure by Intensity, MedDRA System Organ Class and Preferred Term by Age	Safety	U
14.3.3.7	Treatment Emergent Adverse Events Related to Study Product or Injection Procedure by Intensity, MedDRA System Organ Class and Preferred Term by Study Site	Safety	U
14.3.3.8	Treatment Emergent Adverse Events Related to Study Product or Injection Procedure by Intensity, MedDRA System Organ Class and Preferred Term by Fitzpatrick Skin Type	Safety	U
14.3.3.9	Treatment Emergent Adverse Events Related to Study Product or Injection Procedure by Intensity, MedDRA System Organ Class and Preferred Term by Race	Safety	U
14.3.3.10	Treatment Emergent Adverse Events Related to Study Product or Injection Procedure by Intensity, MedDRA System Organ Class and Preferred Term by Gender	Safety	R
14.3.3.11	Treatment Emergent Adverse Events Related to Study Product or Injection Procedure by Intensity, MedDRA System Organ Class and Preferred Term by Prior Botulinum Toxin Use	Safety	R
14.3.4	Summary of Duration of Adverse Events Related to Study Product or Injection Procedure by System Organ Class and Preferred Term	Safety	U
14.3.5	Summary of Number of Days to Onset of Adverse Events Related to Study Product or Injection Procedure by System Organ Class and Preferred Term	Safety	R
14.3.6	Summary of Action Taken for Treatment Emergent Adverse Events Related to Study	Safety	U

2021-02-05 13:16

Effective date:

Effective

Version: 1.0

Table Number	Table Title	Analysis Population	(U)nique/ (R)epeat

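### Neither document requires or analyses where a local adverse event occurred, although 236 of 413 subjects have one area injected with QM1114-DP and the other with placebo

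*Protocol*

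**What the plan says.** **Design.** Protocol section 3 describes four arms. The LCL-alone arm is "60 units QM1114-DP (60 units in the LCL and placebo in the GL, 118 subjects". Its mirror image, the GL-alone arm, also has 118 subjects and reverses the two products. The combination arm (118) has active product in both areas, and the placebo arm (59) has it in neither.

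Protocol 6.1.1 and 6.1.2 give six injection points in the LCL areas and five in the GL area, for active product and placebo alike.

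**Collection.** Protocol 7.2.6.2.1 wants each event "described on the AE form of the eCRF along with the date of onset, severity, relationship to the study product, and outcome". The same sentence adds that no requested and known information may be left out, and the next allows further information to be asked for in some circumstances. Location is not named.

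**Causality.** Protocol 7.2.6.1.7 defines a reasonable possibility as a link between "The study product (active or placebo) and the AE", or between a protocol procedure and the event. The eCRF then asks two yes/no questions, one on the study product and one on its injection procedure (repeated in SAP 1.5.1). Neither is asked by area. A yes to either makes the event related.

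**Analysis.** SAP 2.5.2 summarizes adverse events by treatment group, system organ class and preferred term, with intensity, causality, action taken, onset and duration. The main table of related events is titled "Treatment Emergent Adverse Events Related to Study Product or Injection Procedure by Intensity, MedDRA System Organ Class and Preferred Term". SAP 2.5.2.1 splits related events by age, gender, prior toxin use, race, skin type and study site. The local-spread table (14.3.7.1) is by intensity, class and term. No adverse event table or listing is by GL or LCL. Efficacy, by contrast, is analysed by area (SAP 2.4.1), and the LCL is scored on each side separately (SAP 1.3.1 and 1.3.2).

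**The concern.** A subject in a single-area arm has one active and one placebo area. A bruise, swelling or pain is counted in that arm whichever area it arose in. Some preferred terms show the location, such as eyelid ptosis; a generic injection-site term does not.

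The safety objective (Protocol 2.1.4) covers 60 U in the LCL and 50 U in the GL, separately and together, and the protocol itself links local risks to areas: eyelid ptosis to GL injection, lateral mouth drop and asymmetrical smile to LCL injection (6.1.7.1). A reader will want the local event rate for an area given QM1114-DP and the rate for the same area given placebo. The planned tables supply neither.

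**Working it through.** **1. Counts.** The plan's total is reproduced: 118 + 118 + 118 + 59 = 413. Subjects with one active and one placebo area: 118 + 118 = 236, and 236/413 = 57%. Placebo points are 5 of 11 (45%) in the LCL-alone arm and 6 of 11 (55%) in the GL-alone arm.

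**2. What mixing does to the arm-level comparison.** Let a be the risk of a local event in an area given QM1114-DP and b the risk in an area given placebo, with the areas independent. The documents give no such risks, so a and b are assumed and varied.
- Any local event, single-area arm: 1 − (1 − a)(1 − b)
- Any local event, placebo arm: 1 − (1 − b)²
- Arm-level risk difference: (a − b)(1 − b), against a − b for the area itself
- Share of the arm's local events arising in the placebo area: b/(a + b)

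Example, a = 5%, b = 2%: 1 − 0.95 × 0.98 = 6.90%; 1 − 0.98² = 3.96%. The difference is 2.94 points against 3.0. The ratio is 6.90/3.96 = 1.74 against 2.5. The share is 2/7 = 29%.

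**3. Precision.** SE = √[p₁(1 − p₁)/n₁ + p₀(1 − p₀)/n₀].
- Arm level, 118 vs 59, at 6.90% and 3.96%: √(0.000544 + 0.000645) = 3.4 points.
- Same area, pooled over arms. GL: GL-alone plus combination, 118 + 118 = 236, against LCL-alone plus placebo, 118 + 59 = 177. The LCL counts are the same. At 5% and 2%: √(0.000201 + 0.000111) = 1.8 points.

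| Assumed a, b | Risk difference (points): area / arm level | Relative risk: area / arm level | Share from placebo area | SE (points): same area pooled / arm level |
|---|---|---|---|---|
| 3%, 1% | 2.0 / 2.0 | 3.0 / 1.99 | 25% | 1.3 / 2.6 |
| 5%, 2% | 3.0 / 2.9 | 2.5 / 1.74 | 29% | 1.8 / 3.4 |
| 10%, 5% | 5.0 / 4.8 | 2.0 / 1.49 | 33% | 2.5 / 5.0 |
| 10%, 2% | 8.0 / 7.8 | 5.0 / 2.98 | 17% | 2.2 / 3.9 |

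**4. Where the precision comes from.** At 5% and 2%, knowing the location but keeping 118 vs 59 gives √(0.0475/118 + 0.0196/59) = 2.7 points. So location alone takes the SE from 3.4 to 2.7, and pooling takes it to 1.8.

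**5. A caution on pooling.** The other area is active in 118/236 = 50% of the active group but in 118/177 = 67% of the placebo group. If product in one area can cause events that appear in the other, the pooled groups are not balanced for it. Stratifying by product in the other area removes this. For GL the strata are GL-alone vs placebo (118 vs 59) and combination vs LCL-alone (118 vs 118). With Mantel-Haenszel weights n₁n₀/(n₁ + n₀), 39.3 and 59 (0.4 and 0.6), the SE at 5% and 2% is √(0.16 × 0.000735 + 0.36 × 0.000569) = 1.8 points, so stratifying costs almost nothing.

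**The case against.** The strongest reply is that the randomized safety comparison is intact. All arms are injected at all 11 points in the same way, so needle-related background from the second area is also in the placebo arm, and the risk difference barely moves (2.9 against 3.0 points). The stated objective compares regimens with placebo, and arm-level tables answer that. This stands. A reader might infer that placebo-area events bias the single-area arms against QM1114-DP; the documents do not support that. Such an event is counted in an arm labelled with both products, not as an effect of the active area.

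Second, the form may already hold location. The list in Protocol 7.2.6.2.1 is not exhaustive: the SAP analyses action taken and suspected toxin spread, which that list omits. The eCRF is not in the documents. This stands too. It cannot be said that location is not collected, only that neither document requires or analyses it.

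Third, relatedness is asked twice, and the procedure question suits a bruise or needle pain. That is correct, but neither question identifies the area, and the planned related-event tables merge the two answers.

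Fourth, the examination form records eyelid position, eyebrow position and vision with details, and local spread has its own table and listing. This helps for spread, but assigns no event to GL or LCL.

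Fifth, a reader might infer that the single-area arms offer a clean within-subject contrast of active and placebo. They do not: within each such arm product is confounded with anatomy and with the number of points (five against six). A spread effect may also appear away from the area that caused it.

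**Conclusion.** The gap is real and modest. Neither document requires or analyses the location of local events, while 57% of subjects have one area of each kind. The arm-level comparison with placebo remains valid. What is lost is the local event rate for a treated area, an undiluted relative risk, and precision: over the assumed risks, the arm-level standard error is about 1.8 to 2.0 times that of the same-area comparison (3.9/2.2 to 5.0/2.5).

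These sizes rest on assumed per-area risks and on independence of the areas. Pooling over arms also assumes that product in one area does not alter local events in the other, unless the comparison is stratified. No primary efficacy result is touched. The change should be made because it is cheap and the design already supplies the comparison.

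**What to change.** 1. **Location.** Record GL, LCL right, LCL left or elsewhere for each local or injection-site event. If the eCRF already holds this, nothing is needed. If not, add one field to the AE form, or code location blind from the verbatim term before database lock, with queries where the term is silent.
2. **Table.** In SAP 2.5.2 add a descriptive table of local treatment-emergent events for each area, by the product given in that area. GL: GL-alone plus combination against LCL-alone plus placebo. LCL: LCL-alone plus combination against GL-alone plus placebo. Show it by arm as well, and stratify any pooled difference by the product given in the other area.
3. **Causality.** Show study-product-related and injection-procedure-related events separately; both answers are already collected.
4. **Limits.** Do not make the within-subject GL-against-LCL contrast the main comparison, and footnote that spread effects may not arise from the area where they appear.

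The cost is site instruction and a few queries if a field is added, and one or two extra tables. Arms, visits, endpoints and significance level are unchanged.
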